2.1 Data analysis general information

Novartis will perform the primary and final analyses.

Analyses will be based on this document and performed using SAS® Version 9.4 (SAS Institute, Inc., Cary, NC) or later.

Categorical data will be presented as frequencies and percentages. For continuous data, the number of non-missing observations, mean, standard deviation, median, minimum, and maximum will be presented. For selected parameters, 25th and 75th percentiles may also be presented. Summary tables will be presented by visit when applicable.

All efficacy endpoints will be summarized descriptively using observed values and change from baseline at each visit, in addition to the analyses mentioned in the respective sections below.

The analysis will be primarily focused on period 1. However, subject disposition, study treatment exposure and prednisolone exposure will be also summarized for period 2. All safety analyses will also be performed for subjects who received OAV101 during either period 1 or period 2.

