2.1.1 General definitions

Study treatment is OAV101 (1.2x10¹⁴ vector genomes) or sham administration.

The **date of first administration of study treatment** is defined as the date of OAV101/sham administration during Treatment Period 1.

The **date of second administration of study treatment** is defined as the date of OAV101/sham administration during Treatment Period 2.

Study day is the number of days since the date of first administration of study treatment for period 1 and number of days since the date of second administration of study treatment for period 2.

- Study day 1 is the date of the first administration of study treatment during Treatment Period 1 and the date of second administration of study treatment during Treatment Period 2 .
- Study day of date X = date X – date of first administration of study treatment during Treatment Period 1 + 1 if date X is on or after the date of first administration of study treatment during Treatment Period 1.
- Study day of date X = date X – date of first administration of study treatment during Treatment Period 1 if date X is before the date of first administration of study treatment during Treatment Period 1. Study days before the first study treatment administration during Treatment Period 1 will have the prefix “-”.

Baseline is defined as follows:

- **HFMSE**: Baseline value for HFMSE (i.e., total or individual item) score is defined as the average of HFMSE (i.e., total or individual item) score used for stratification (maximum of all available values before baseline visit) and the measurement or evaluation made at the baseline visit prior to the first administration of study treatment during Treatment Period 1, assuming both values have complete and valid scores available. If just one of the above mentioned values (score used for stratification and baseline visit measurement) has a complete and valid score available, then the baseline HFMSE (i.e., total or individual item) score is defined as the single available value.

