- **RULM**: Baseline value for RULM total score is defined as the average of all non-missing assessments prior to the first administration of study treatment during Treatment Period 1, assuming all assessments have complete and valid total scores available. If two of the assessments have a complete and valid total score available, then the baseline RULM total score is defined as average of the two available assessment scores. If just one of the assessments has a complete and valid total score available, then the baseline RULM total score is defined as the single total score available.
- **Other assessments**: The latest non-missing measurement or evaluation made prior to the first administration of study treatment during Treatment Period 1.

Change from baseline is defined as post-baseline value minus baseline value.

For HFMSE and RULM, the **End of Follow-up Period 1** assessment is defined as the average of the Week 48 and Week 52 assessments, assuming both assessments have complete and valid total / individual scores available. If just one of the assessments collected at these two visits has a complete and valid total / individual score available, then the end of Follow-up Period 1

assessment is defined as the single assessment total / individual score collected at Week 48 or Week 52.

Last participation day can be calculated using end of participation date – date of second administration of study treatment + 1.

Inexact values will be handled as follows.

- If a laboratory value is recorded/reported as “>X”, “≥X”, “- If an antibody titer value is reported as <12.5, a value of 0.5×12.5 will be used and if ≥ 819200 is reported, a value of 1.5×819200 will be used for analysis purposes. The originally recorded values will be displayed in corresponding listings.

An **Adverse Event** (AE) is any untoward medical occurrence in a clinical investigation participant, which does not necessarily have a causal relationship with the drug or device under study.

A Treatment Emergent Adverse Event (TEAE) is any AE whose onset or worsening occurred after dosing on Day 1 till the end of follow-up period 2.

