2.1.2 Analysis visit windows

Unless otherwise specified, **analysis visit windows** for efficacy and safety assessments which are summarized on a by-visit basis are defined based on study day post dosing. For by-visit endpoints, the time windows describe how data will be assigned to protocol-specified time points during follow up.

Period 2 windows defined below will be used for analyses of “on or after OAV101 administration” (i.e., OAS).

The analysis windows for respective assessments are as follows:

Vital Signs and Neurological Examination:

Period 1 windows:

Visit	Nominal day	Start day	End day
Day 1	Day 1	Day 1	Day 1
Day 2	Day 2	Day 2	Day 2
Day 3	Day 3	Day 3	Day 3
Week 1	Day 8	Day 4	Day 11
Week 2	Day 15	Day 12	Day 18
Week 3	Day 22	Day 19	Day 25
Week 4	Day 29	Day 26	Day 36
Week 6	Day 43	Day 37	Day 50
Week 8	Day 57	Day 51	Day 64

Visit	Nominal day	Start day	End day
Week 10	Day 71	Day 65	Day 78
Week 12	Day 85	Day 79	Day 99
Week 16	Day 113	Day 100	Day 127
Week 20	Day 141	Day 128	Day 155
Week 24	Day 169	Day 156	Day 183
Week 28	Day 197	Day 184	Day 211
Week 32	Day 225	Day 212	Day 239
Week 36	Day 253	Day 240	Day 267
Week 40	Day 281	Day 268	Day 295
Week 44	Day 309	Day 296	Day 323
Week 48	Day 337	Day 324	Day 351
Week 52	Day 365	Day 352	Week 52 + Day 1 – 1

Period 2 windows:

Visit (OAV-SHAM)	Visit (SHAM-OAV)	Nominal day	Start day	End day
Week 52 + Day 1	Day 1	Day 1	Day 1	Day 1
Week 52 + Day 2	Day 2	Day 2	Day 2	Day 2
Week 52 + Day 3	Day 3	Day 3	Day 3	Day 3
Week 53	Week 1	Day 8	Day 4	Day 11
Week 54	Week 2	Day 15	Day 12	Day 18
Week 55	Week 3	Day 22	Day 19	Day 25
Week 56	Week 4	Day 29	Day 26	Day 36
Week 58	Week 6	Day 43	Day 37	Day 50
Week 60	Week 8	Day 57	Day 51	Day 64
Week 62	Week 10	Day 71	Day 65	Day 78
Week 64	Week 12	Day 85	Day 79	Last participation day

Body Weight:

Period 1 windows:

Visit	Nominal day	Start day	End day
Day 1	Day 1	Day 1	Day 1
Day 2	Day 2	Day 2	Day 2
Week 1	Day 8	Day 3	Day 18

Visit	Nominal day	Start day	End day
Week 4	Day 29	Day 19	Day 43
Week 8	Day 57	Day 44	Day 71
Week 12	Day 85	Day 72	Day 99
Week 16	Day 113	Day 100	Day 127
Week 20	Day 141	Day 128	Day 155
Week 24	Day 169	Day 156	Day 183
Week 28	Day 197	Day 184	Day 211
Week 32	Day 225	Day 212	Day 239
Week 36	Day 253	Day 240	Day 267
Week 40	Day 281	Day 268	Day 295
Week 44	Day 309	Day 296	Day 323
Week 48	Day 337	Day 324	Day 351
Week 52	Day 365	Day 352	Week 52 + Day 1 – 1

Period 2 windows:

Visit (OAV- SHAM)	Visit (SHAM- OAV)	Nominal day	Start day	End day

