2.2 Analysis sets

The **Intent to Treat Analysis Set (ITT)** comprises all randomized participants, regardless of whether they were dosed with study treatment during Treatment Period 1. Participants will be analyzed according to the treatment/procedure they have been assigned to.

The **Full Analysis Set (FAS)** comprises all randomized participants who were dosed with study treatment during Treatment Period 1. Participants will be analyzed according to the treatment/procedure they have been assigned to.

As per the protocol, participant randomization occurs approximately 2 weeks prior to when treatment administration/sham procedure is planned to occur. There is a possibility that a participant is randomized but subsequently becomes ineligible for the trial during this time and ultimately would not be dosed with the study treatment or contribute to the post-treatment study assessments. In order to account for this possibility, the FAS will exclude participants who were randomized but were not dosed with the study treatment.

The **Active Treatment Period 2 Set (ATP2)** comprises all participants who were dosed with the study treatment during Treatment Period 2. Summaries of data using ATP2 will be based on actual treatment/treatment sequence.

The **OAV101 Treated Analysis Set (OAS)** comprises all randomized participants who were dosed with OAV101 treatment during Treatment Period 1 or 2. Participants will be analyzed according to the treatment/procedure they have been assigned to.

The **Safety Analysis Set (SAF)** includes all participants who were dosed with the study treatment during Treatment Period 1. Participants will be analyzed according to the study treatment/procedure received.

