2.3 Patient disposition, demographics and other baseline characteristics

2.3.1 Patient disposition

Disposition will be presented for all participants, and will include the following summaries:

- The number and percentage of participants who were screened and who subsequently failed screening, along with the reasons for screen failure will be summarized.
- The number and percentage of participants randomized and included in each analysis set (ITT, FAS, ATP2, OAS, SAF). Percentages will be based on the number of randomized participants.
- The number and percentage of participants in the ITT who:
 - Completed Follow-up Period 1, defined as all participants with a Week 52 visit conducted either remotely or at the study site
 - Discontinued prior to the end of Follow-up Period 1 and the associated reason for discontinuation
 - Completed Follow-up Period 1 and continued to Treatment Period 2
 - Completed Follow-up Period 1 and did not enter Treatment Period 2 and the associated reason for not entering Treatment Period 2

The above summary will be produced by Treatment Period 1 treatment group (OAV101, sham) and overall, and separately broken out by age subgroup (≥ 2 to < 5 years, ≥ 5 to < 18 years) within each treatment group.

- The number and percentage of participants in the ATP2 who:
 - Completed Follow-up Period 2, defined as all participants with a Week 64 visit conducted either remotely or at the study site
 - Discontinued prior to the end of Follow-up Period 2 and the associated reasons for discontinuation

The above summary will be produced by treatment sequence across Treatment Periods 1 and 2 (OAV101/sham, sham/OAV101) and overall, and separately broken out by age subgroup (≥ 2 to < 5 years, ≥ 5 to < 18 years) within each treatment sequence.

A listing of participant disposition will be produced.

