2.4.2 Prior, concomitant and post therapies

Prior and concomitant medications and significant non-drug therapies taken prior to and after the start of the study treatment will be listed and summarized according to the World Health Organization Drug Dictionary (WHODD) Anatomical Therapeutic Chemical (ATC) classification system. The dictionary version used will be noted in the summary tables and listings.

A prior medication is defined as any medication taken prior to the date of the administration of study treatment during Treatment Period 1. A concomitant medication is defined as any medication that started prior to the date of the administration of study treatment during Treatment Period 1 and continued to be taken after the administration of study treatment during Treatment Period 1 or any medication that started on or after the date of the administration of study treatment during Treatment Period 1. With this approach, a medication may be classified as both prior and concomitant.

The number and percentage of participants taking prior medications in the ITT and concomitant medications in the SAF through the end of Follow-up Period 1 will be summarized by ATC2 and generic drug name based on the WHODD by overall.

A second summary will be produced to detail the concomitant medications initiated after dosing with OAV101 through the end of Follow-up Period 2. This summary will combine all concomitant medications taken by participants who were treated with OAV101 during Treatment Period 1 or 2. For participants who underwent the sham administration procedure during Treatment Period 1 and received OAV101 during Treatment Period 2, only medications initiated after dosing during Treatment Period 2 will be included.

Listings will be produced to summarize the prior and concomitant medications taken throughout the study. The listing of concomitant medications will include all medications taken through the end of Follow-up Period 2.

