2.7.3 Laboratory data

Safety laboratory data and genetic diagnosis laboratory data analyzed by both the central laboratory as well as by local labs will be utilized for safety analyses. The SAF will be used for all summaries of data.

Values at each scheduled visit as well as change from baseline values to each post-baseline visit through the end of Follow-up Period 1 will be summarized for each protocol-specified chemistry, hematology, and liver function test laboratory parameter using descriptive statistics for Treatment Period 1 treatment group (OAV101, sham). Normalized values (observed absolute values/ULN) for ALT, AST, ALP, total bilirubin and troponin-I and absolute values for platelets at each scheduled visit as well as change from baseline in absolute values to each post-baseline visit through the end of Follow-up Period 1 will be visualized on a box plot. Listings of hematology (all platelet values and out of range values for all other parameters), chemistry (out of range values for all parameters), urinalysis (out of range values for all parameters), and hepatic laboratory data meeting elevation criteria data will also be produced. Listings of liver imaging, if performed will also be produced.

In addition, shift tables based on CTC grade (CTCAE version 5) will be provided for all laboratory parameters that were defined in the [\[Novartis Internal Guidance on CTCR Grading of Lab Parameter\]](#) (e.g., platelets, alanine aminotransferase (ALT), aspartate aminotransferase (AST), alkaline phosphatase (ALP), gamma glutamyl transferase, and serum total bilirubin, etc.) to compare a participant's baseline laboratory evaluation relative to the post-baseline values. For laboratory (serum) parameters Glutamate Dehydrogenase and Troponin I, shift tables will be produced by below, within, or above the normal range level based on normal ranges of the laboratory used in this study (Low/Normal/High).

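### For sham-first participants, the post-OAV101 safety tables restart study day and visits at the OAV101 dose but keep the pre-sham baseline

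*SAP*

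**What the plan says.** SAP 2.1.1 gives HFMSE and RULM their own baselines. For all other assessments, baseline is "The latest non-missing measurement or evaluation made prior to the first administration of study treatment during Treatment Period 1". The same section defines the first administration as the Period 1 procedure, whether OAV101 or sham.

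SAP 2.1 then plans a further set of safety outputs: "All safety analyses will also be performed for subjects who received OAV101 during either period 1 or period 2". For these outputs, three things are tied to the OAV101 dose:

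- **Study day.** In Period 2 it is the "number of days since the date of second administration of study treatment for period 2" (SAP 2.1.1).
- **Visit labels.** SAP 2.1.2 states "Period 2 windows defined below will be used for analyses of" data on or after OAV101. For the sham-then-OAV101 sequence, Week 53 is relabelled Week 1, and so on to Week 12.
- **Included values.** SAP 2.7.3, 2.7.4.1 and 2.7.4.2 admit only values on or after OAV101 dosing.

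Those sections still refer to baseline and do not redefine it. The only visible reset is the updated baseline in SAP 5.6, for pulse and weight at age 18 or older.

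**The concern.** A table of change after OAV101 is read as change from the participant's state just before OAV101. For OAV101-first participants it is that. For sham-first participants, the label says Week 1 after OAV101 while the comparison value precedes the sham, about a year earlier. A QTcF increase, a newly met QTcF category, a troponin I shift or a weight flag could then arise wholly during the sham year. Change in the opposite direction during that year could mask a real one. Cardiac adverse events are among the important risks in Protocol 4.5.3 and are an AESI category, so the ECG and troponin I tables matter most.

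**Working it through.** The plan states no figure for the age of the reference value, so there is none to reproduce. The check is to trace the definition through each output and compute the age.

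**Age of the reference at the OAV101 dose.** Under the SAP 2.1.1 study-day rule there is no Day 0. Study day d (positive) lies d - 1 days after the Period 1 procedure, and study day -k lies k days before it. Protocol Table 8-1 puts the Week 52 + 1 Day dose at Day 366, which is 365 days after the Period 1 procedure.

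| Reference value | Calculation | Age at dose (days) |
|---|---|---|
| Day -1 | 365 + 1 | 366 |
| Screening Visit 1, Day -60 to -45 (window +15) | 365 + 60; 365 + 45 | 425; 410 |
| Week 48, Day 337 ± 7 | 365 - 329; 365 - 343 | 36; 22 |
| Week 52, Day 365 | 365 - 364 | 1 |

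Protocol 8.4.8 supports an ECG at the Baseline visit. Day -1 is an assumption for laboratory and weight rows not visible in Table 8-1; a pre-dose weight on Day 1 would give 365. The only visible pre-treatment troponin I mark is at Screening Visit 1, hence 410 to 425 days if it is not repeated. At Week 64 (Day 449, 83 days after the dose) the ages are 366 + 83 = 449 days, and 410 + 83 = 493 to 425 + 83 = 508 days.

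**Closer values exist.** The SAP 2.1.2 windows include Week 52 for ECG, hematology and chemistry, weight, height and BMI. Troponin I has a Week 48 window that runs to the day before the Period 2 procedure.

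**Which post-OAV101 outputs use baseline.**

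| Output | Effect of the old baseline |
|---|---|
| ECG change, newly met QTcF categories, maximum QTcF increase (SAP 2.7.4.1) | Affected |
| Troponin I low/normal/high shift (SAP 2.7.3) | Affected |
| Under-18 weight flag (SAP 5.6, via 2.7.4.2) | Affected; uses BMI-for-age categories, so growth is partly allowed for |
| CTCAE shifts without paired numeric limits, e.g. AST and ALP | Affected |
| ALT, GGT, total bilirubin, GLDH and platelet shifts | Little affected |
| Multiples-of-ULN counts, ECHO counts, TEAE and AESI incidence, absolute vital-sign cut-offs | Not affected |

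The split among laboratory shifts comes from eligibility. Besides platelets and ALT, SAP 2.7.3 names "aspartate aminotransferase (AST), alkaline phosphatase (ALP), gamma glutamyl transferase, and serum total bilirubin" as examples for CTCAE grading. ALT, total bilirubin, GGT and GLDH above ULN exclude at Screening Visit 1 (Protocol 5.2, exclusion 12) and again at Week 48 (Protocol 3, Period 2 exclusion 6). Platelets below LLN exclude at both points (exclusion 25; Period 2 exclusion 12). Either baseline then gives mostly the same starting category, apart from retests or change before dosing. Isolated AST elevation is expressly allowed at both points, and ALP has no numeric limit.

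**The case against.** Several counter-arguments have weight.

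- **Sham-year change is visible elsewhere.** SAP 2.7.3 and 2.7.4.1 tabulate Period 1 change and shifts by treatment group, so the sham group's movement to Week 48 or 52 can be read beside the later tables. This helps with mean changes. It does not resolve individual maximum, worst-value or newly-met categories.
- **Individual data are not absent.** SAP 2.7.4.1 names no ECG listing, and a reader might infer that individual ECG values cannot be checked. The documents do not support that: Protocol 3 promises tables and listings for Follow-up Period 2, and the SAP Introduction covers listings of all data. Clinically significant ECG abnormalities are also recorded as history or AEs (Protocol 8.4.8).
- **Eligibility narrows the laboratory effect further.** Clinically significant laboratory abnormalities exclude at entry and at Week 48, by investigator judgement. That reduces the AST, ALP and troponin I problem but does not remove it.
- **The stakes are limited.** The outputs are descriptive, the analysis focuses on Period 1, and Protocol 3 bars Treatment Period 2 data from endpoint analyses.
- **Redaction.** Parts of the SAP are blacked out and the table shells are not public, so an output-level baseline may exist. The general definition in 2.1.1 is readable, however, and that is where the rule belongs.

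Two stronger readings are tempting. A reader might infer that sham-first participants contaminate a pooled column, up to 50/125 = 40% of it. Pooling is not stated. The OAV101-treated set covers those "dosed with OAV101 treatment during Treatment Period 1 or 2. Participants will be analyzed according to the treatment/procedure they have been assigned to", and Protocol 12.5.2 presents tables by treatment group. Among the post-OAV101 outputs, only the medication summary is expressly merged: "This summary will combine all concomitant medications taken by participants who were treated with OAV101 during Treatment Period 1 or 2".

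A reader might also count spurious QTcF cases. Take an illustration with every input assumed: no drug effect, visit SD 8 msec, linear one-year drift SD 10 msec, 45 sham-first and 75 OAV101-first participants. About 10.4 participants would show a maximum increase above 30 msec. About 7.0 of these (75 × 9.4%) are OAV101-first, whose baseline is correct. Moving the baseline lowers the total to 7.7, a fall of 2.7, and with zero drift it changes nothing. Most of that count reflects longer follow-up after OAV101 (about 64 versus 12 weeks), which is a separate matter.

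**Conclusion.** The gap in the definition is real on the readable text. If the SAP is followed as written, the baseline-dependent post-OAV101 outputs for sham-first participants use a reference 366 days old at dosing, or 410 to 425 days for troponin I, when values 1 day or 22 to 36 days old are scheduled. This rests on nominal visit days, on a Day -1 value for rows not visible in Table 8-1, and on no re-anchoring in the redacted text or shells.

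The effect on the tables cannot be sized. The documents give neither drift nor visit-to-visit variability for the affected measures, and without drift there is no effect. The randomized comparison and the main safety counts stand. Severity is minor to moderate: worth correcting because the tables would be misread, not because any confirmatory conclusion depends on them.

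**What to change.** Add one sentence to SAP 2.1.1: *For post-OAV101 (OAS) outputs, baseline is the latest non-missing value before the participant's first OAV101 dose.* Apply it to the baseline-dependent outputs in SAP 2.7.3, 2.7.4.1, 2.7.4.2 and 5.6. OAV101-first participants keep the baseline they have now. Keep the Period 1 baseline for all Period 1 comparisons.

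Confirm that the OAS outputs are displayed by sequence, as SAP 2.3.1 already does for Period 2 disposition: "by treatment sequence across Treatment Periods 1 and 2 (OAV101/sham, sham/OAV101) and overall".

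The cost is one definition, one derived baseline flag and, if not already planned, by-sequence columns. No new data are needed. A version of the maximum and worst-value tables limited to the first 12 weeks after OAV101 in both sequences is optional. It addresses unequal follow-up rather than this gap and drops later OAV101-first data, so it would sit beside the full-follow-up tables.
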